#### 7. STUDY TREATMENTS

## 7.1. Investigational and Reference Treatments

Study drug in this study includes fasinumab, naproxen, and their matching placebo. Fasinumab and its matching placebo are SC study drug. Naproxen and its matching placebo are oral study drug.

Fasinumab drug product is supplied for this study in the following concentrations:

- Fasinumab 2 mg/mL: Each 1 mL single use pre-filled syringe delivers 0.5 mL of a 2 mg/mL solution (1 mg dose) of study drug
- Fasinumab-matching placebo: Each 1 mL single use pre-filled syringe delivers 0.5 mL of placebo solution

Naproxen 500 mg capsules and naproxen-matching placebo capsules will be provided by the sponsor.

#### Year 1

At the baseline visit of Year 1, patients will be randomized 3:3:3:1 to receive 1 of the following treatment regimens:

- Fasinumab 1 mg SC Q4W and naproxen-matching placebo oral, twice daily
- Fasinumab 1 mg SC Q8W (patients will receive placebo injections at the study visits where study drug is not administered) and naproxen-matching placebo oral, twice daily
- Fasinumab-matching placebo SC Q4W and naproxen 500 mg oral, twice daily
- Fasinumab-matching placebo SC Q4W and naproxen-matching placebo oral, twice daily

All patients will receive SC injections of fasinumab or fasinumab-matching placebo. All SC injections will be in the abdomen, thigh, or upper arm. Patients will be observed in the clinic for approximately 1 hour after study drug is administered. Patients randomized to earlier versions of the protocol with 3 mg Q4W or 6 mg Q8W fasinumab were discontinued from study drug for the remainder of the study and moved directly into the follow-up period.

Naproxen 500 mg or naproxen-matching placebo will be administered orally, twice daily. A proton pump inhibitor or other gastric protective medication may be prescribed if deemed medically necessary by the investigator or sub-investigator.

Doses of SC study drug must be given within  $\pm 7$  days from the scheduled dose date. If the window is missed, the SC dose of fasinumab or fasinumab-matching placebo should not be administered, however the oral dose of naproxen or naproxen-matching placebo will be dispensed. The next SC dose of fasinumab or fasinumab-matching placebo should be administered at the next scheduled dosing date.

Detailed instructions for study drug dose administration are provided in the pharmacy manual.

Year 2

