#### 7.3.2.1. Reasons for Permanent Discontinuation of Study Drug

As of 17 August 2020, all patients in the Year 2 Treatment Period must be immediately discontinued from study drug, undergo all End of Treatment visit assessments, and move directly into the 20-week safety follow-up period.

Prior to 17 August 2020, study drug dosing was to be permanently stopped in the event of any of the following:

- A patient who is currently enrolled under an earlier version of this protocol must be immediately discontinued from study drug, undergo all end of treatment visit assessments, and move directly into the 20-week safety follow-up period under this version of the protocol, if they meet any of the following conditions that were excluded after re-evaluating the safety profile of NSAIDs:
  - They have a known medical history (at any time) of peripheral vascular disease, transient ischemic attack, cerebrovascular accident, myocardial infarction, unstable angina, or documented atherosclerotic cardiovascular disease; or
  - They have a known GFR <30 mL/minute/1.73m^2 or,
  - They are currently taking combination therapy of a diuretic with either an ACE inhibitor or ARB (Note: Patients may remain in the study if they are willing and able to change their antihypertensive regimen such that they are no longer on a combination of a diuretic with either an angiotensin-converting enzyme (ACE) inhibitor or angiotensin receptor blocker (ARB)
- A patient who was randomized under an earlier version of the protocol to 3 mg Q4W or 6 mg Q8W fasinumab
- A patient developing clinically significant peripheral sensory or motor neurologic events confirmed by a neurologist's examination and graded by the neurologist as at

least moderate peripheral neuropathy limiting activities of daily living (ADL), ie, grade ≥2 according to Common Terminology Criteria for Adverse Events (CTCAE) v.4; study sites should use CTCAE v.4 criteria throughout the study for consistency

- Evidence of pregnancy
- A patient developing new or worsening signs and symptoms indicative of carpal tunnel syndrome
- Continued non-compliance with protocol-defined maximum acetaminophen/paracetamol use (with a maximum daily dose of 2500 mg [countries where 500 mg strength tablets / capsules are available] or 2600 mg [countries where 325 mg strength tablets / capsules are available]) during the treatment and follow-up periods, after appropriate counseling

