# 11.2. Electronic Systems

Electronic systems that may be used to process and/or collect data in this study will include the following:

- IVRS / IWRS system randomization and study drug supply
- Rave Medidata EDC system clinical data capture
- SAS
- A pharmacovigilance and clinical safety software system collection and reporting of SAEs and AESIs
- Electronic Clinical Outcome Assessment systems collect patient-reported outcome or patient clinical assessment results

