## USM Analysis

WOMAC pain and physical function will be summarized descriptively based on the USM Analysis set. No sensitivity analysis will be conducted using the USM analysis set.

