### **Data from Year 2**

The following endpoints were collected in Year 2:

- WOMAC
- EQ-5D-5L
- WPAI-OA
- Rescue Medication Usage

Summary statistics for the above variables will be presented by treatment group for each visit in Year 2 based on the SAF – Year 2. For numeric endpoints, the raw, change from Year 1 baseline value and change from Year 2 baseline values will be summarized. No models will be fit to the data, nor will any statistical analysis be performed comparing treatment arms or statistics derived from statistical models.

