## **6.5. Visit Windows**

By-visit analysis (including laboratory data, vital signs, ECG, ADA) will be summarized by the nominal visit number. Assessments taken outside of protocol allowable windows will be displayed according to the case report form (CRF) assessment recorded by the investigator. For assessments without a nominal visit number such as Unscheduled, End-of-Treatment (EOT), and End-of-Study (EOS)/Early Termination (ET) assessments, a visit number will be assigned based on the actual visit date using the study day analysis window based on the targeted visit study day in Section 10.2 Schedule of Time and Events. The following visit windows will be used to map the unscheduled visits, EOT and EOS /ET visits and eCOA assessments based on the study day:

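### SAP 6.5 files eCOA scores by study day from first dose, so off-drug WOMAC follow-up scores of patients stopped by sponsor action can be labelled as treatment visits, including Week 104E

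*SAP*

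**What the plan says.** SAP 6.5 has two rules. The general one is "By-visit analysis (including laboratory data, vital signs, ECG, ADA) will be summarized by the nominal visit number". It then adds that the windows in SAP Tables 1 and 2 "will be used to map the unscheduled visits, EOT and EOS /ET visits and eCOA assessments based on the study day". Both tables count days from first dose. In SAP Table 2 the windows for Weeks 52E to 104E cover every day from 352 to 743. Week 108E follows at 744 to 813 and Week 124E at 814 to 967. No window depends on whether the patient is still on treatment. WOMAC is patient-reported, and Protocol 11.2 describes the relevant system: "Electronic Clinical Outcome Assessment systems collect patient-reported outcome or patient clinical assessment results".

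Two groups left treatment by sponsor action and skipped the remaining treatment visits.

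- Protocol 7.3.2.1: "As of 17 August 2020, all patients in the Year 2 Treatment Period must be immediately discontinued from study drug". These patients are to "undergo all End of Treatment visit assessments, and move directly into the 20-week safety follow-up period".
- Protocol 7.1: patients randomized to 3 mg Q4W or 6 mg Q8W "were discontinued from study drug for the remainder of the study and moved directly into the follow-up period".

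The protocol's schedules of events place WOMAC at both follow-up visits (Weeks 56 and 72; Weeks 108E and 124E). During Year 2 treatment they place it only at Weeks 64E, 76E, 88E and 104E.

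On analysis, SAP 5.7.6 (Data from Year 2) states: "Summary statistics for the above variables will be presented by treatment group for each visit in Year 2". SAP 5.7.1 (USM Analysis) states: "WOMAC pain and physical function will be summarized descriptively based on the USM Analysis set". Neither mentions off-treatment scores.

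**The concern.** The windows fit a patient who is treated to Week 52 or Week 104E and then followed up. For a patient moved into follow-up earlier, the calendar and the visit sequence part company. The visit is a follow-up visit, but its study day lies in a treatment-visit window. Because these patients attend no further treatment visits, no on-treatment score competes for the slot.

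No other part of the SAP catches this. SAP 5.7.1 excludes post-discontinuation data from the Year 1 primary efficacy analysis only. The on-treatment and post-treatment periods in SAP Section 5 are defined for safety variables.

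Change in WOMAC at visits from Week 52E to 104E is a listed exploratory endpoint (SAP 4.5.3, item 8), and Protocol 3.2.1 says Year 2 efficacy is assessed to monitor risk-benefit. A score taken 20 weeks after treatment ended, shown as the end-of-treatment visit with no flag, misdescribes long-term effect.

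**Working it through.** **Inputs.** The windows and target days come from SAP Table 2. The follow-up spacing is not stated for an early stop. I infer it from the target days: 757 − 729 = 28 and 869 − 729 = 140. Protocol 6.2.3 closes Year 2 entry to patients whose Week 52 visit falls on or after 26 March 2020, so the last entry is about 25 March. That is 145 days before 17 August, which puts the earliest stop at about day 365 + 145 = 510.

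**Reproducing the windows.** Each upper bound is the midpoint of adjacent target days, rounded down. For Week 104E this is (729 + 757)/2 = 743, and for Week 108E (757 + 869)/2 = 813. All 16 finite upper bounds in SAP Table 2 agree.

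**Mapping.** With end of treatment on day D, the scores fall on D + 28 and D + 140:

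| D | 4-week score filed as | 20-week score filed as |
|---|---|---|
| 510–519 | 76E | 92E |
| 520–547 | 80E | 96E |
| 548–575 | 84E | 100E |
| 576–603 | 88E | 104E |
| 604–631 | 92E | 108E |
| 632–659 | 96E | 108E |
| 660–673 | 100E | 108E |
| 674–687 | 100E | 124E |
| 688–715 | 104E | 124E |
| 716–729 | 108E | 124E |

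Example: D = 589 gives days 617 and 729, the exact targets of Weeks 88E and 104E. The 4-week score has a treatment label whenever D is below 716, and the 20-week score whenever D is below 604. For D from 604 to 673 the 20-week score takes the label of the 4-week follow-up visit.

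**Scores entering a scheduled WOMAC window**, with D uniform on 510 to 729 (220 days):

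- 4-week: 10 days (76E) + 28 (88E) + 28 (104E) = 66; 66/220 = 30%.
- 20-week: 28 days (104E); 28/220 = 12.7%.

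The other treatment-labelled scores go to 80E, 84E, 92E, 96E and 100E, where no WOMAC is scheduled.

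**Sensitivity to the ±7-day visit window.**

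- Visits 7 days late: (3 + 28 + 28)/220 = 27% of 4-week scores.
- Visits 7 days early: (17 + 28 + 28)/220 = 33% of 4-week scores.
- The 20-week figure stays at 28/220 in both cases. The stop days feeding Week 104E move to 569–596 (late) or 583–610 (early).

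**Stopped doses.** In SAP Table 1 the Week 52 window ends at day 393. On the same spacing, the 4-week score has a Year 1 treatment label for D up to 393 − 28 = 365, and the 20-week score for D up to 393 − 140 = 253 (Week 36). The documents give no stop days for these 285 patients.

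**The case against.** **Nominal visit governs.** SAP 6.5 opens with nominal visit numbers and introduces the windows for assessments that lack one; Visits 31E and 32E have one. This is arguable, but it leaves the explicit mention of eCOA assessments without effect. At best the text is ambiguous.

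**Timing.** The SAP implements Amendment 8, and the August 2020 stop came with Amendment 9. That explains the Year 2 gap but does not close it, and SAP Section 1 allows revision for amendments. The 3 mg and 6 mg stop predates the SAP.

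**Low consequence.** This stands. Year 2 efficacy is descriptive, with no models or treatment comparisons.

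**Off-drug scores are already there by design.** Patients who stop for other reasons are asked to keep attending treatment visits, so treatment-visit rows already contain off-drug scores. This stands against limiting all treatment-visit WOMAC to a period after the last dose, which would be a choice of estimand. It does not justify giving a follow-up visit a treatment-visit name.

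**Stronger readings that the documents do not support.**

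- A reader might infer that most of the Week 104E row would be off drug. The row also holds patients who reached Week 104E before 17 August 2020, and the documents do not count them.
- A reader might count every follow-up score with a treatment label as mixed with on-drug data. Many of them land at visits with no scheduled WOMAC.
- A reader might infer that the fasinumab effect is understated. All arms, including naproxen prn, were stopped and are mapped alike, so no direction is shown.

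**Conclusion.** The point holds as a labelling error that should be corrected. Followed literally, SAP 6.5 files some off-drug follow-up WOMAC scores as treatment visits. The 30% and 12.7% figures describe only patients stopped on 17 August 2020. They rest on the inferred 28- and 140-day spacing and on uniform stop days, neither of which the documents state. The 20-week score is the firm case. The 4-week score is less clearly off drug, particularly under Q8W dosing.

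The reach is limited to descriptive Year 2 WOMAC and, if it is tabulated by visit, WOMAC in the urgent safety measure set; the USM paragraph does not specify by-visit tables. The co-primary analysis excludes post-discontinuation data, and the treatment policy analysis uses such data on purpose.

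**What to change.** In SAP 6.5, state that eCOA records from follow-up visits keep their nominal follow-up visit (18/19, 31E/32E), or are windowed from end of treatment, and are never assigned to a treatment-visit window. If the Year 1 treatment policy analysis is meant to place such scores by study day, name that as an exception. In the Year 2 summaries (SAP 5.7.6) and the USM summaries (SAP 5.7.1), show follow-up scores separately or flag them as off treatment. No blanket restriction by time since last dose is needed.

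The cost is SAP wording and one derivation rule, with no new data. Fewer patients will appear at the later Year 2 treatment visits.

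In the same edit, check SAP Table 1. Its Week 52 window (352 to 393) contains the Week 56 target day, 393, and the Week 56 window (394 to 463) does not.

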**Table 1: Year 1 Analysis Windows**

Visit Number	Visit Name	Targeted Study Daysa	Analysis Window in Study Days
1	Screen	Day -30 to Day -11	[-30, -11]
2	Pre-randomization	Day -10 to -7	[-10, -1]
3	Baseline	1	1
Phone 1	Week 1	8	[2, 11]
4	Week 2	15	[12, 22]
5	Week 4	29	[23, 43]
6	Week 8	57	[44, 71]
7	Week 12	85	[72, 99]
8	Week 16	113	[100, 127]
9	Week 20	141	[128, 155]
10	Week 24	169	[156, 183]
11	Week 28	197	[184, 211]
12	Week 32	225	[212, 239]
13	Week 36	253	[240, 267]
14	Week 40	281	[268, 295]
15	Week 44	309	[296, 323]

Visit Number	Visit Name	Targeted Study Days a	Analysis Window in Study Days
16	Week 48	337	[324, 351]
17	Week 52	365	[352, 393]
18	Week 56	393	[394, 463]
19	Week 72	505	[464, 603]
Phone 2	Week 100	701	≥ 604

a Study days are calculated from the first dose of study drug (Day 1).

**Table 2: Year 2 Analysis Windows**

Visit Number	Visit Name	Targeted Study Days a	Analysis Window in Study Days
17E	Week 52E	365E	[352, 379]
18E	Week 56E	393E	[380, 407]
19E	Week 60E	421E	[408, 435]
20E	Week 64E	449E	[436, 463]
21E	Week 68E	477E	[464, 491]
22E	Week 72E	505E	[492, 519]
23E	Week 76E	533E	[520, 547]
24E	Week 80E	561E	[548, 575]
25E	Week 84E	589E	[576, 603]
26E	Week 88E	617E	[604, 631]
27E	Week 92E	645E	[632, 659]
28E	Week 96E	673E	[660, 687]
29E	Week 100E	701E	[688, 715]
30E	Week 104E	729E	[716, 743]
31E	Week 108E	757E	[744, 813]
32E	Week 124E	869E	[814, 967]
Phone 2E	Week 152E	1065E	≥ 968

a Study days are calculated from the first dose of study drug (Day 1).

If multiple measurements occur within the same visit window, the following rules will be used to determine the analysis value:

- When multiple valid measurements occur within the same visit window, the one closest to the target study day will be used in the analysis.

- When multiple valid measurements occur within equal distance from the target study day, the value after the target study day will be used in the analysis.

Both scheduled and unscheduled measurements will be considered for determining abnormal/PCSV values from laboratory, vital sign or ECG as well as the baseline values.

## **6.6. Unscheduled Assessments**

The determination of baselines and values at the end of treatment for both efficacy and safety variables will be based on scheduled available assessments and unscheduled available assessments.

Extra assessments (laboratory data or vital signs associated with non-protocol clinical visits or obtained in the course of investigating or managing adverse events) will be included in listings, but not summaries except for the endpoint determination. If more than one laboratory value is available for a given visit, the first observation will be used in summaries and all observations will be presented in listings.

## **6.7. Pooling of Centers for Statistical Analyses**

Study centers will be pooled according to their geographic region the statistical analysis. The geographic regions are:

- Europe: Bulgaria, Denmark, France, Germany, Hungary, Italy, Lithuania, Poland, Romania, Russia, Spain, Ukraine, United Kingdom
- North America: United States
- Rest of World: South Africa

## **6.8. Statistical Technical Issues**

Not applicable.

## **7. INTERIM ANALYSIS**

No interim analysis of efficacy data from Year 1 will be conducted prior to collection of all data necessary for the the primary and secondary analysis.

A first-step analysis of all available efficacy and safety data for Year 1 and select analysis of available Year 2 safety data will be performed when all data for Year 1 Treatment Period (baseline through week 52) have been collected and validated for all randomized patients.

Another analysis will be performed for regulatory purposes on the remaining Year 1 WOMAC and PRO assessments and safety data (collected during the Year 1 follow-up period) and any Year 2 efficacy and safety data available at the time of the data cut-off for the second analysis.

Additional analyses of other efficacy and safety data may be performed for regulatory purposes as needed.

Individuals unblinded to patient-level data for the first-step or any subsequent analyses will no longer be involved in the day-to-day conduct of the ongoing study. Patient-level results will not be released to any site-facing personnel or anyone who is directly involved in the conduct of the study.

## **8. SOFTWARE**

All analyses will be done using SAS Version 9.4.

## 10. APPENDIX

### 10.1. Summary of Statistical Analyses

#### Efficacy Analysis:

Endpoint	Analysis Populations	Primary Analysis	Statistical Method	Supportive Analysis	Subgroup Analysis	Other Analyses
Primary Endpoint						
Co-primary: - Change from baseline in the WOMAC pain subscale scores - Change from baseline in the WOMAC physical function subscale score	mFAS, FAS, PPS	Change from baseline at Week 16 in the WOMAC pain subscale scores & Change from baseline at Week 16 in the WOMAC physical function subscale scores	MMRM with multiple imputation	Sensitivity Analyses: - Treatment Policy Estimand - Tipping Point Analysis - Analysis using the PPS	Subgroups: K-L Category, Index Joint, Region, Age Group, Sex, Weight, BMI Group.	For Non-flare patients - Change from baseline at Week 16 in the WOMAC pain subscale scores & Change from baseline at Week 16 in the WOMAC physical function subscale scores
Secondary Endpoints						
Change from baseline in WOMAC pain subscale scores	mFAS, FAS, PPS	Change from baseline at Week 44 in the WOMAC pain subscale scores	MMRM with multiple imputation	Sensitivity Analyses: - Treatment Policy Estimand - Analysis using the PPS	Subgroups: K-L Category, Index Joint, Region, Age Group, Sex, Weight, BMI Group.	Change from baseline at all other visits in the WOMAC pain subscale scores
Change from baseline in WOMAC physical function subscale scores	mFAS, FAS, PPS	Change from baseline at Week 44 in the WOMAC physical function subscale scores	MMRM with multiple imputation	Sensitivity Analyses: - Treatment Policy Estimand - Analysis using the PPS	Subgroups: K-L Category, Index Joint, Region, Age Group, Sex, Weight, BMI Group.	Change from baseline at all other visits in the WOMAC physical function subscale scores

Endpoint	Analysis Populations	Primary Analysis	Statistical Method	Supportive Analysis	Subgroup Analysis	Other Analyses
Change from baseline in WOMAC pain subscale scores averaged across multiple timepoints	mFAS, FAS	Change from baseline in WOMAC pain subscale scores averaged across Weeks 4, 8, 12 and 16	ANCOVA with multiple imputation			Change from baseline in WOMAC pain subscale scores averaged across Weeks 36,40 and 44
Change from baseline in WOMAC physical function subscale scores averaged across multiple timepoints	mFAS, FAS	Change from baseline in WOMAC physical function subscale scores averaged across Weeks 4, 8, 12 and 16	ANCOVA with multiple imputation			Change from baseline in WOMAC physical function subscale scores averaged across Weeks 36,40 and 44
Change from baseline in PGA scores	mFAS, FAS	Change from baseline at Week 44 in the WOMAC physical function subscale scores	MMRM with multiple imputation			Change from baseline at all other visits in PGA scores
Proportion of patients with <math>\geq 30\%</math> improvement in WOMAC pain subscale	mFAS, FAS	Proportion of patients with <math>\geq 30\%</math> improvement in WOMAC pain subscale at Week 16	CMH Test			NA

**Safety Analyses:**

Endpoint	Analysis Populations	Primary Analysis	Statistical Method	Supportive Analysis	Subgroup Analysis	Other Analyses
Treatment Emergent Adverse Events	SAF – Year 1 & SAF – Year 2	Percent of patients by system organ class and preferred term	Descriptive Statistics	No	No	Percent of patients by system organ class, preferred term and severity
Treatment Emergent Serious Adverse Events	SAF – Year 1 & SAF – Year 2	Percent of patients by system organ class and preferred term	Descriptive Statistics	No	No	NA
Treatment-related Treatment Emergent Adverse Events	SAF – Year 1 & SAF – Year 2	Percent of patients by system organ class and preferred term	Descriptive Statistics	No	No	Percent of patients by system organ class, preferred term and severity
Treatment Emergent Adverse Events of Special Interest	SAF – Year 1 & SAF – Year 2	Percent of patients by system organ class and preferred term	Descriptive Statistics	No	No	No
Treatment Emergent Adverse Events Leading to Discontinuation from Study Drug	SAF – Year 1 & SAF – Year 2	Percent of patients by system organ class and preferred term	Descriptive Statistics	No	No	No
Treatment Emergent Non-Serious Adverse Events	SAF – Year 1 & SAF – Year 2	Percent of patients by system organ class and preferred term	Descriptive Statistics	No	No	No
Clinical Laboratory Measurements	SAF – Year 1 & SAF – Year 2	Actual and Change from baseline values	Descriptive Statistics	PCVS Analysis	No	No
Vital Sign Measurements	SAF – Year 1 & SAF – Year 2	Actual and Change from baseline values	Descriptive Statistics	PCVS Analysis	No	Incidence of Orthostatic Hypotension
12-Lead ECGs	SAF – Year 1 & SAF – Year 2	Actual and Change from baseline values	Descriptive Statistics	PCVS Analysis	No	Shift Table Analysis

Endpoint	Analysis Populations	Primary Analysis	Statistical Method	Supportive Analysis	Subgroup Analysis	Other Analyses
Physical & Neurological Exams	SAF – Year 1 & SAF – Year 2	Number of patients with new-onset abnormal examination findings	Descriptive Statistics	NA	No	No
Survey of Autonomic Symptoms	SAF – Year 1 & SAF – Year 2	Number of patients reporting the presence of each symptom/health problem	Descriptive Statistics	Number of Symptoms Reported  Total Symptom Impact Score	No	No
Adjudicated Arthropathy	SAF – Year 1 & SAF – Year 2	Number of patients requiring adjudication  Number of patients with adjudicated arthropathy  Number of patients with destructive arthropathy	Descriptive Statistics	Time to AA  Time to DA  Break-down by subtypes of AA	No	No
Joint Replacements	SAF – Year 1 & SAF – Year 2	Number of patients with joint replacements	Descriptive Statistics	Time to JR	No	No

